### Treatment run-in

The TRI feature of the study will evaluate a policy of treating all eligible patients with adalimumab for 16 weeks but only continuing treatment beyond 16 weeks in the subset that are successfully maintained with inactive disease in both eyes on <=5mg oral prednisolone at 16 weeks.

In accordance with the marketing authorisation for adalimumab, the TRI will commence with an 80mg dose of adalimumab at week 0 using two pre-filled pens under the supervision of a Sciensus Nurse.

Dosing will continue with fortnightly 40mg injections starting one week after the initial dose at weeks 1, 3, 5, 7, 9, 11, 13 and 15 (eight doses in total).

The TRI will end at 16 weeks when response will be assessed. Responders (see 6.3.1) who remain eligible and confirm consent at 16 weeks will be randomly allocated to adalimumab or placebo.

The visit window for the TRI response assessment visit is +7 days only.

### **Randomised trial (RCT)**

RCT dosing will commence 1 week after randomisation, with fortnightly 40mg injections of drug or placebo until the end of the trial (follow-up for between 12 weeks and 170 weeks, about 3 and 40 months).

In the RCT, in the event of TF in either or both eyes, the participant will be offered the opportunity to repeat the TRI. If TF is observed at the final assessment in the RCT, the participant will exit the trial.

The visit window for RCT follow up visits is -14 days to +7 days.

### **Repeat TRI**

TRI dosing will commence 1 week after the date of the response assessment visit, with fortnightly 40mg injections of open label adalimumab for 16-weeks (8 injections in total).

At the end of the 16-weeks the participant's response will be assessed again. If the participant shows a response to treatment as per section 6.3.1, they can re-enter the RCT. If they do not respond, then they will exit the trial.

The visit window for the TRI response assessment visit is +7 days only.

### **Repeat RCT**

Responders will re-enter the RCT and their allocation will be switched in relation to their last allocation (i.e. in RCT1 if entering RCT2, or RCT2 if entering RCT3), maintaining masking (see section 5.1).

Dosing will commence 1 week after the date of the response assessment visit and continue with fortnightly 40mg injections of drug or placebo to the end of the trial.

The visit window for RCT follow up visits is -14 days to +7 days.

In the event of TF in either or both eyes, participants will be offered the opportunity to repeat the TRI for a third time, repeating the above process (if classified as a responder at the end of the TRI, then entering RCT3). Participants can restart the TRI and subsequently switch RCT allocation twice.

### **OLE**

Participants who consent to OLE at their last RCT before 31st January 2025.

For the OLE, irrespective of the number of switches, those on adalimumab at the time of unmasking will receive open-label drug. Dosing will commence 1 week after the date of the response assessment at the final RCT visit and continue with fortnightly 40mg injections of open label drug until they either experience TF or they reach the end of the trial (last patient visit that occurs before 31st March 2026).

Those on placebo will receive no treatment but still attend study visits.

The visit window for OLE follow up visits is -14 days to +7 days. Participants will continue to follow the visit schedule started in the RCT.

Details of the drug are described in the summary of product characteristics (SmPC; Appendix 1) for Imraldi™. The manufacture, quality assurance, labelling and packaging of the placebo are described in the IMP dossier.

### **Missed injection date**

If an injection date is missed, the advice to patients is to administer the missed injection immediately upon remembering. The patient should then adhere to their original injection schedule, i.e. administer their next injection 2 weeks after the date their previous injection was due had they not taken a dose late.

**Delayed doses can be taken at any point up until 2 days before the next one is due (i.e., doses cannot be on consecutive days).**

### **Intraocular surgery**

Participants who experience TF within 14 days of having intraocular surgery (day of surgery is day 0) during the RCT should continue in the RCT and OLE as if the TF had not occurred (because the TF is assumed to be related to the surgery). These participants should continue to administer the IMP and be followed up at their next scheduled visit. Clinicians can prescribe a single course of oral steroids or intravenous methylprednisolone (maximum of 8-week course) peri or post operatively as would be prescribed in usual care to prevent relapse. Ozurdex can also be prescribed as would be used in usual care. Any additional medication required as treatment for the surgery will be documented on the medication CRF.

If TF criterion or criteria continue(s) beyond 14 days (except >5mg/day oral prednisolone to prevent relapse due to surgery) then true TF has occurred and the participant should restart the TRI.

If participants undergo intraocular surgery during the initial or repeat TRI they will exit the TRI and re-enter when their condition has stabilised after surgery. Intraocular surgery should be reported as an adverse event.

In accordance with standard care for adalimumab, if a patient acquires an infection or serious illness during the trial, the treating clinician may advise the patient to temporarily cease the study medication until it is considered safe to resume administration.

### **Storage & dispensing**

Study medication will be stored by a central NHS pharmacy department in accordance with Good Clinical Practice and pharmacy department SOPs. Study medication will be transferred from the central NHS pharmacy to a third party organisation (Sciensus, formerly called

Healthcare at Home Ltd) to dispense the medication and distribute it directly to participants' homes.

### **Accountability**

Drug accountability including stock control, ordering, and prescribing will be managed by a software application securely accessed by authorised study personnel [57]. Study medication will not be stored at participating NHS sites prior to dispensing. Participants will return the packaging of used study medication and any unused pens to the local hospital site for accountability and destruction by the research team. Used study medication pens will be disposed of in sharps bins by the participants at home. Sciensus are responsible for providing and disposing of sharps bins.

### **Participant training & delivery**

Sciensus will use their network of trained nurses to deliver training to participants in their homes about self-administration of the study medication at the start of the TRI period. In exceptional circumstances participants can receive training from appropriately qualified staff at their referring hospital. This must be discussed with the trial team prior to participant enrolment and have approval from both the PI and the CI.

Sciensus will use their fully traceable, cold-chain supply network to deliver study medication to participants' homes for the duration of the trial. Sciensus deliver commercial Imraldi™ and train patients who receive the drug as part of standard NHS care and as such are experienced in providing these services and have processes in place for reporting AEs or issues with specific pre-filled pens to patients' care teams (i.e. hospital sites).

Both the IMP and placebo will be labelled in accordance with Annex 13. The contents of the label will be submitted to the MHRA for approval. Storage of the IMP, both drug and placebo, will be in accordance with the SmPC/dossier (Appendix 1). The IMP will be accounted for according to NHS pharmacy standards.

### **Reference safety information**

The SmPC Imraldi 40mg solution for injection in a pre-filled pen, Section 4.8 dated 16 Aug 2021, will be used as the reference Safety Information (RSI).

In accordance with the SmPC, participants cannot be administered live vaccines for the duration of their time on the trial intervention.

## **5.8 Primary and secondary outcomes**

### ***5.8.1 Primary outcome***

The primary outcome is time to the first treatment failure (TF), for a participant, i.e. TF may occur in either eye and may be triggered by incident ANIU in an eye that did not previously have ANIU. TF is defined as a composite of standard criteria reflecting clinical decision-making, including visual acuity and clinical signs of active inflammation which have been used successfully in other ANIU trials [1, 4, 58].

Our definition of TF will modify the composite endpoint used in the VISUAL trials [1,2] by: (i) excluding isolated anterior uveitis as a TF event (it can be treated effectively and safely with low dose, low frequency topical CS); and (ii) including a clinically important deterioration in CMO as a TF event [11], because it is an ANIU complication causing visual loss in a third of patients [59] which has often studied as a TF event in other trials of ANIU.

Participants will be assessed for TF at each visit after randomisation.

Any of the following criteria in one or both eyes, where applicable, will constitute TF:

- i.  $\geq 15$  letter decrease in best corrected visual acuity (BCVA), compared to BCVA measured by an optometrist masked to treatment allocation at the 16 week TRI visit;
- ii. new active inflammatory chorioretinal lesions (masked review of fundus colour and autofluorescence images by clinician during the RCT; unmasked during the OLE);
- iii.  $>20\%$  increase in central macular thickness (CMT), compared to CMT at the 16 week TRI timepoint (CMT is a parameter that is measured by an automated algorithm when doing optical coherence tomography (OCT));
- iv. onset or worsening of retinal vasculitis (masked clinician assessment of fundus fluorescein angiogram during the RCT; unmasked during the OLE);
- v. 2 step worsening of vitreous haze compared to score at the 16-week TRI visit (masked clinician assessment during the RCT; unmasked during the OLE);
- vi. prescription by a masked clinician of  $>5\text{mg/day}$  oral prednisolone to maintain uveitis remission (i.e. to avert relapse before any of the above criteria for manifest active disease (i-v) during the RCT; unmasked during the OLE).

Prescription of  $>5\text{mg/day}$  oral prednisolone for a co-morbidity (e.g. rheumatic disease) but with none of i-v being present does not constitute TF.

If the participant experiences any of criteria i-vi within 14 days of having intraocular surgery, it does not constitute TF. If the criteria persists beyond 14 days (except  $>5\text{mg/day}$  oral prednisolone) then it does constitute TF.

The arrangements for managing a participant's continued follow-up in the trial following TF have been described above, including switching treatment allocation without unmasking allocation (see 5.1 and 5.7).

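### The 14-day surgery exemption is written per participant and names no eye, so a treatment failure found in the unoperated eye is postponed or lost from the primary endpoint

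*Protocol*

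**What the plan says.** Protocol section 5.8.1 defines the outcome for the participant, with either eye able to trigger it: "TF may occur in either eye and may be triggered by incident ANIU in an eye that did not previously have ANIU". The list of criteria opens in the same way: "Any of the following criteria in one or both eyes, where applicable, will constitute TF". Criteria i-v (acuity, chorioretinal lesions, macular thickness, vasculitis, vitreous haze) are findings in an eye. Criterion vi (prednisolone above 5 mg/day) belongs to the participant.

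The exemption at the end of section 5.8.1 reads: "If the participant experiences any of criteria i-vi within 14 days of having intraocular surgery, it does not constitute TF". The Intraocular surgery paragraph of section 5.7 says the same for trial conduct: "Participants who experience TF within 14 days of having intraocular surgery (day of surgery is day 0) during the RCT should continue in the RCT". It gives its reason in brackets: "because the TF is assumed to be related to the surgery".

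Both places add a persistence rule. Section 5.8.1 begins it "If the criteria persists beyond 14 days" and section 5.7 begins it "If TF criterion or criteria continue(s) beyond 14 days"; in both, the failure then counts, apart from prednisolone above 5 mg/day. Section 5.7 confines that exception to prednisolone given against a surgery-related relapse, and allows one systemic steroid course of at most 8 weeks. Section 5.8.1 attaches neither a reason nor a duration. On timing, section 5.7 says: "These participants should continue to administer the IMP and be followed up at their next scheduled visit".

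**The concern.** The outcome looks at both eyes, but the exemption is triggered by an operation on one eye and switches off both. Its only stated justification is that surgery caused the failure. That fits the operated eye. The protocol does not argue that it extends to the other eye, nor does it restrict the rule to the operated one.

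A new lesion or vasculitis in the unoperated eye on day 10 is therefore, on the text, not TF. A genuine first event would be postponed or dropped from the primary analysis for a reason that does not describe it. Sites that read the purpose rather than the words could also classify the same event differently.

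**Working it through.** **1. The passages side by side.**

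- Unit of the outcome (5.8.1): participant, failure in either eye.
- Unit of the exemption (5.8.1 and 5.7): participant, any of criteria i-vi, no eye named.
- Reason (5.7): failure attributed to the surgery.
- Recovery route (both): criteria i-v still present beyond 14 days count as TF.
- Reassessment (5.7): next scheduled visit, with no check fixed at day 14. Visits are 12-weekly to week 48 and 16-weekly after that (5.3).

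For criteria i-v found in the unoperated eye within the window there are two outcomes. If they persist past day 14, TF is recorded, but later than first seen. If they settle before anyone re-examines the eye, no TF is recorded. A systemic steroid course permitted around surgery would also reach the unoperated eye, so the second outcome is possible.

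**2. The plan's own sample size.** Inputs from sections 5.9 and 1.1: HR 0.5, 90% power, two-sided 5%, 27% against 52% TF-free at 12 months, 10% loss.

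- Freedman events: (1.960 + 1.282)² × ((1 + 0.5)/(1 − 0.5))² = 10.51 × 9 = 94.6, so 95.
- Mean event probability: (0.73 + 0.48)/2 = 0.605.
- Evaluable participants: 95/0.605 = 157.02, so 158.
- With 10% loss: 158 × 1.1 = 173.8, so 174; or 158/0.9 = 175.6, so 176.

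The stated 174 is reproduced.

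**3. Chance of a failure in any 14-day window.** Constant hazards are assumed.

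- Placebo: −ln(0.27) = 1.309 per year; 1 − exp(−1.309 × 14/365.25) = 4.9%.
- Adalimumab: −ln(0.52) = 0.654 per year; 1 − exp(−0.654 × 14/365.25) = 2.5%.

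**4. Expected unoperated-eye failures in a window.** Assumptions, none of them in the protocol: a share *s* of the 174 has one operation while still TF-free, operations are equally common in both arms, and half of the hazard belongs to the other eye. Halving the hazard gives 2.48% and 1.25%, mean 1.86%. The expected count is 174 × *s* × 0.0186.

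| Assumed *s* | Participants with surgery | Unoperated-eye failures in a window |
|---|---|---|
| 2% | 3.5 | 0.06 |
| 5% | 8.7 | 0.16 |
| 10% | 17.4 | 0.32 |
| 20% | 34.8 | 0.65 |

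These count every failure arising in a window. To be affected, a failure must also be found within the 14 days; to be lost, it must then settle before it is rechecked.

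**5. Effect on power.** With 10% lost, expected events are 174 × 0.9 × 0.605 = 94.7, and Freedman power is Φ(√94.7/3 − 1.96) = 90.1%. Dropping 1% of events (0.95 of an event, more than any row above) gives 89.8%.

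**The case against.** The strongest reply is that the persistence rule already protects the endpoint. Much of that stands. A reader might infer that unoperated-eye failures are struck out altogether; the documents do not support this, because criteria i-v lasting beyond day 14 count. Only those that settle are lost.

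Three further inferences also go too far:

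- **A delay of up to 17 weeks.** That figure is the widest gap between scheduled visits (5.3), not the time from event to detection. Section 6.3 and the Table 1 footnote on unscheduled visits call for a full assessment whenever TF is suspected between visits. It remains true that section 5.7 points the exempted participant to the next scheduled visit and fixes no check at day 14.
- **An open-ended steroid exemption.** Section 5.8.1 alone could be read so, but section 5.7 deals with the same situation and sets both a purpose and an 8-week ceiling. What is left is an inconsistency between the two sections.
- **A bias or loss of power.** The rule is the same in both arms and is applied by masked staff during the RCT. The counts above are under one event, and nothing in the documents establishes a direction of bias.

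It can also be said that limiting the reason to the operated eye is inference, since section 5.7 does not say so. That is fair. But if the sponsor holds that surgery on one eye explains failure in the other, the protocol should state it; at present it is silent.

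Finally, TF stops the IMP and restarts open-label adalimumab (5.1), so rewriting section 5.7 would alter clinical management. This stands, and it limits what the fix may ask for.

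**Conclusion.** The defect is real and narrow. The endpoint definition covers both eyes, while the exemption covers the whole participant on a ground that fits one eye, and no other section corrects this. Affected events are re-dated if they persist and lost if they settle.

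The size is probably under one event: 0.06 to 0.65 for 2% to 20% of participants having surgery, with constant hazards and half of failures in the other eye. The surgery rate and the split between eyes are assumptions, so these figures show scale only. The case for change is the validity and consistent application of the primary endpoint, at almost no cost. It does not rest on power or on a demonstrated effect on the hazard ratio.

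**What to change.** - **Section 5.8.1, endpoint definition.** Limit the exemption for criteria i-v to the operated eye. Criteria i-v in the other eye are then judged as on any other day. Keep criterion vi, which has no side, at participant level.
- **Sections 5.7 and 5.8.1.** Reconcile them on which eye and which steroid prescription the exemption covers. How such participants are managed and whether they continue IMP is for the sponsor to decide; this point proposes no rule.
- **Cases already recorded.** Apply the clarified endpoint rule only by masked review before the RCT part of the database is locked. The assessors must be masked to allocation, since participants are unmasked at their last RCT visit. If that is no longer possible, keep the existing classification for the primary analysis and report the eye-level rule as a sensitivity analysis.

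The cost is a few words in section 5.8.1, a reconciliation of two paragraphs through an amendment, and a check of TF records for participants who had surgery. Those participants can be found, because section 5.7 asks for intraocular surgery to be reported as an adverse event. The main risk is reclassifying people who were managed under the existing rule, which is why masking and timing matter.

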### 5.8.2 Secondary outcomes

Secondary outcomes will include:

- a) Individual TF components, assessed at each trial visit;
- b) Retinal morphology (OCT; macular and retinal nerve fibre layer), assessed at each trial visit;
- c) AEs, assessed at each trial visit;
- d) HRQoL measured using the EQ-5D-5L questionnaire [3][7] at the start of TRI, at 16 weeks immediately before randomisation, then 12-weekly after randomization up to week 48 and 16-weekly thereafter;
- e) Patient-reported symptoms of side-effects at the start of TRI, at 16 weeks (immediately before randomisation), then at each trial visit after randomisation and at any interim attendance prompted by an AE;
- f) Patient-reported visual function [2], at the start of TRI, at 16 weeks immediately before randomisation, 12-weekly up to week 48 and 16 weekly thereafter;
- g) Best corrected visual acuity (BCVA) assessed at each trial visit;
- h) Employment status at the start of TRI, at 16 weeks immediately before randomisation, 12-weekly up to week 48 and 16 weekly thereafter;
- i) Resource use at the start of TRI, at 16 weeks immediately before randomisation, and every 12 weeks (up to week 48) or 16 weeks (after week 48) during follow-up after randomisation.

## 5.9 Sample size justification

We hypothesise that participants randomised to receive adalimumab will have a lower risk of TF than those allocated to receive placebo. The sample size has been chosen to test this hypothesis. In estimating the sample size, we have considered the results observed in previous studies; hazard ratios (HRs) for time to first TF in two previous trials of adalimumab (in patients with active and inactive ANIU, respectively) were 0.50 and 0.57 [1, 4]. As our study will only randomise participants who are found to respond to treatment in the TRI phase, we anticipate that we will observe a greater benefit than in these trials, which included both responders and non-responders. Therefore, we have set the target HR at 0.5. Assuming that 27% in the placebo group survive free from TF 12 months after randomisation (estimated from placebo groups of the two trials with 40% active and 60% inactive disease), we have set a target sample size of 174 randomised participants. A study of this size will have 90% power to detect a HR 0.5 at a 5% two-sided significance level, allowing for 10% loss-to-follow-up in the first 12 months.

## 6. Trial methods

### 6.1 Description of randomisation

Eligibility will be checked, and consent obtained to the whole study at the beginning of the TRI, with both being confirmed at the 16-week visit when responder status has been ascertained and eligibility for the trial has been confirmed. Randomisation will be carried out at this visit so that the appropriate IMP can be prescribed at the same time. Randomisation will be performed by a member of the local research team on the delegation log who is authorised to do so using a secure internet-based randomisation system ensuring allocation concealment. Participants will be allocated in a 1:1 ratio to either adalimumab or placebo.

The random allocations will be computer-generated by a statistician in the trials unit in blocks of varying size (unknown to trial personnel) and stratified by centre, before the trial starts to recruit. The allocations will be embedded in the trial database and concealed from all clinical and research personnel until a participant has been recruited. Key data to characterise a participant's current clinical status at will be collected at the time of randomisation.

### 6.2 Masking and unmasking

During the RCT, participants, their clinical care team (i.e. their ophthalmologist and other members of eye care team) and the research nurse(s) responsible for participant follow-up, will all be masked to participants' allocations. Except for the study statistician, clinical trials staff managing the trial will also be masked to allocation. The randomisation system will provide a unique code which the study pharmacy (Sciensus, formerly called Healthcare at Home, Ltd) will use to identify the pens to be dispensed. It will not be possible to distinguish between syringes containing drug and placebo dispensed during the RCT on the basis of their appearance or any other characteristics. No one will be masked during the OLE.

The IMP will be injected subcutaneously by participants at home. The prefilled syringes will look identical and we are not aware of any sensation from self-injection of adalimumab that will differ from injection of placebo. Adalimumab may induce side-effects in some patients that will inadvertently unmask participants. We acknowledge this may be a limitation of the study. We will collect information to document the extent to which this happens.

Participants will be made aware before entering the study that they will not be told which treatment they will receive during the RCT. Doctors will prescribe the 'study medication' with a unique code; appropriate pens, corresponding to the code, will be dispensed to participants. Bristol Trials Centre (BTC) and other designated personnel will be able to break the code in the

event of an emergency but will not know the allocation in the usual course of dispensing a prescription for trial IMP.

If clinically indicated (i.e. in the event of a serious adverse event (SAE) requiring knowledge of the allocation for treatment) the treatment allocation will be unmasked by the BTC during office hours or by the on-call pharmacist at UHBW. Unmasking will be done using the secure web-based IMP-Track IMP management and accountability system [57]. Only authorised personnel will have access to the IMP-Track system. Any request for unmasking will be fully documented, recording the identity of the person asking for the allocation to be unmasked and the reason for unmasking. Instances of unmasking will be monitored throughout the trial.

